Outcomes after Hypotensive Neuraxial Anesthesia in Total Hip Arthroplasty

FUNDER: Department of Anesthesiology

PROTOCOL NO.: 2018-2235

VERSION & DATE: 12/5/2018

TABLE OF CONTENTS

| | |
|---|----------|
| TABLE OF CONTENTS | 2 |
| PROTOCOL SYNOPSIS | 3 |
| 2.0 INTRODUCTION..... | 5 |
| 3.0 OBJECTIVE(S) OF CLINICAL STUDY | 5 |
| 4.0 STUDY HYPOTHESES | 6 |
| 5.0 STUDY DESIGN | 6 |
| 5.1 Endpoints | 6 |
| 5.1.1 Primary Endpoint | 6 |
| 5.1.2 Secondary Endpoints..... | 6 |
| 5.2 Study Sites | 6 |
| 6.0 STUDY POPULATION | 6 |
| 6.1 Number of Subjects..... | 6 |
| 6.2 Inclusion Criteria..... | 7 |
| 6.3 Exclusion Criteria | 7 |
| 7.0 PROCEDURES..... | 7 |
| 7.1 Data Collection | 7 |
| 8.0 STATISTICAL ANALYSIS..... | 8 |
| 9.0 ADVERSE EVENT ASSESSMENT | 8 |

PROTOCOL SYNOPSIS

| | |
|--------------------------------|--|
| Protocol Title: | Outcomes after Hypotensive Neuraxial Anesthesia in Total Hip Arthroplasty |
| Protocol Number: | 2018-2235 |
| Protocol Date: | |
| Sponsor: | Department of Anesthesiology |
| Principal Investigator: | [name], PhD |
| Objective: | The proposed project will be the largest study on deliberate hypotensive neuraxial anesthesia and adverse outcome in THA. It will provide essential feedback and guidance to our clinical practice, indicating whether we need to modify our intraoperative management for better patient outcomes and less adverse complications, or conversely may allow us to argue that deliberate hypotensive neuraxial anesthesia is not associated with adverse events. This will be the first significant database study to examine the clinical outcomes of patients undergoing THA with a deliberative hypotensive neuraxial anesthetic technique. |
| Study Design: | Retrospective study |
| Enrollment: | 10,000 |
| Subject Criteria: | All primary THA patient data with sufficiently complete intraoperative vital signs will be included in the study. |
| Data Collection: | Sources: Medical record Variables: 
• MRN• Age• BMI• ASA status• Ethnicity• Gender/sex• zip code• insurance• type of surgery• primary anesthetic type• anesthetic procedures• anesthesia provider name• anesthesia provider helpers (CRNA, Resident, Fellow)• surgeon• duration of surgery• duration of anesthesia |

| | |
|------------------------------|--|
| | 
• Problem list of comorbidities (OSA, COPD, asthma, HTN, HLD, CAD, CHG, arrhythmia, pulmonary hypertension, DM (type 1 or 2), coagulopathy, hx of dvt/PE, anxiety, depression, bipolar disorder, schizophrenia, IBS)• Number of allergies• Pre-op medications: betablockers, asa, anticoagulant, NSAID, Opioid, steroids, ACE inhibitor, calcium antagonists and diuretics, blood pressure (pre-op and all intra-op), intra-op medication: TXA IV or topical, ketamine, blood transfusion, albumin, IV fluids, epinephrine, ephedrine, phenylephrine, hydralazine, labetalol,• Laboratory results: hemoglobin, BUN, creatinine (pre-op and first post-op)• Post-operative medications for the first 24 hours: IV fluids, albumin, blood transfusion, epinephrine, ephedrine, phenylephrine, opioids• Complications: MI, CVA, death, ARF, pneumonia, arrhythmia, DVT, PE |
| Statistical Analysis: | 
• Two-step logistic regression modeling to determine odds ratios• Confidence intervals: 95% |

2.0 INTRODUCTION

There have been long debates in regards to the appropriate blood pressure management during joint replacement. Traditionally at HSS, many anesthesiologists routinely manage the blood pressure in the 40-60 mmHg MAP range to minimizing perioperative bleeding and optimize surgical outcome. Such deliberate hypotension anesthesia does not seem to cause increased risk of major complications in several studies, including studies from our institution (Paul et al, Can J Anesth 2007; Bombardieri et al, Anesth Analg, 2016; Weinstein et al. RAPM, 2018).

However, concerns still remain due to evidence from other major studies, which indicated increased complication risks with intraoperative hypotension (Salmasi et al, Anesthesiology, 2017; Sessler et al, Anesthesiology, 2018). Previous studies at HSS are mostly limited by the small number of patients, and therefore could not draw more convincing conclusion. With the implementation of EPIC electronic medical record system at HSS in 2016, it is feasible to access thousands of patients' intra-operative data nowadays. Hereby, we propose this project to study whether there is associated between deliberate hypotension and increased adverse outcomes among primary THA patients. In addition, we will explore whether controlled hypotension continues to be an effective technique for reducing intra-operative blood loss with modern surgical techniques and in the setting of widespread use of tranexamic acid.

3.0 OBJECTIVE(S) OF CLINICAL STUDY

The goal of this study is to determine if hypotensive neuraxial anesthesia is associated with worse outcomes in Primary Total Hip Arthroplasty (THA). There is a substantial body of literature supporting the safety and utility of the practice of deliberate neuraxial hypotension for reduction of blood loss during THA. However, substantial controversy remains regarding the safety of deliberate and controlled intraoperative hypotension with epinephrine mediated cardiac output augmentation as compared to inadvertent and/or uncontrolled intraoperative hypotension. Moreover, it is unclear if advances in surgical practice combined with the widespread use of TXA have diminished the clinical utility of deliberate hypotension as a means of minimizing blood loss. Therefore, this study is looking at the extent and duration of hypotension under neuraxial anesthesia in primary THA surgery.

This proposed project will be the largest study on deliberative hypotensive neuraxial anesthesia and adverse outcome in total hip arthroplasty. It will provide essential feedback and guidance to our clinical practice, indicating whether we need to modify our intra-operative management for better patient outcomes and less adverse complications, or conversely may allow us to argue that deliberate hypotensive neuraxial anesthesia is not associated with adverse events.

We will be accessing and reviewing EPIC data of patients who have undergone Primary Total Hip Arthroplasty at HSS from January 2016- December 3, 2018

4.0 STUDY HYPOTHESES

This is retrospective study hypothesize that:

- A. There is no association between level and duration of hypotension with (i) myocardial infarction (MI), (ii) cerebrovascular accident (CVA), (iii) death in primary total hip arthroplasty patients.
- B. With the use of IV tranexamic acid is administered, the use of deliberate neuraxial anesthesia induced hypotension does not result in a further clinically relevant reduction in calculated blood loss after total hip arthroplasty.

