5.0 STUDY DESIGN

5.1 Endpoints

5.1.1 Primary Endpoint

The primary outcomes are the incidences of:

- i. myocardial infarction (MI)
- ii. cerebrovascular accident (CVA)
- iii. death
- iv. calculated perioperative intraoperative blood loss.

All primary outcomes are events during the inpatients stay.

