7.0 PROCEDURES

The independent variables of interest include extent of intraoperative hypotension (MAP <45, 50, 55, 60 mmHg) and duration of hypotension (5 mins interval). Intraoperative blood loss will be calculated based on pre-operative and post-operative laboratory hemoglobin levels.

The outcome variables include MI, CVA, death, intraoperative blood loss, ARF, pneumonia, arrhythmia, DVT, PE, and number of packed red blood cell (pRBC) transfusions.

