8.0 STATISTICAL ANALYSIS

1. Proposed analysis (e.g., student's t-test, ANOVA, chi-square, regression, etc.):
Two-step logistic regression modeling to determine odds ratios
2. Confidence intervals: 95%
3. Total sample size required: 10,000

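### Hypothesis A treats no association as the result to be supported, but no margin, upper-limit rule or expected precision separates reassurance from an inconclusive result

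*Combined protocol and SAP*

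**What the plan says.** Hypothesis A in Section 4.0 reads "There is no association between level and duration of hypotension with" MI, CVA and death. Section 3.0 opens neutrally, asking whether the technique is associated with worse outcomes. It then names two uses for the result: either practice needs to change, or the study "may allow us to argue that deliberate hypotensive neuraxial anesthesia is not associated with adverse events".

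Section 8.0 has three entries: two-step logistic regression giving odds ratios, 95% confidence intervals, and "Total sample size required: 10,000". The synopsis repeats these and adds no justification. No section gives a margin, a rule for the upper limit, an assumed event rate, power or an expected interval width.

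Three other places bear on the point:

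- Section 2.0 faults earlier work at the site: "Previous studies at HSS are mostly limited by the small number of patients, and therefore could not draw more convincing conclusion".
- Section 5.1.1 limits the events counted: "All primary outcomes are events during the inpatients stay".
- Hypothesis B is worded around relevance, in that hypotension "does not result in a further clinically relevant reduction in calculated blood loss". Hypothesis A has no such qualifier.

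**The concern.** Hypothesis A is the statistical null. A test or interval that fails to reject the null does not establish it; the data may simply be too sparse. To argue for the absence of harm, the interval must exclude every increase that would matter, so that increase has to be named in advance. The planned interval will have an upper limit, but the plan sets no value to judge it against.

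No sentence in the plan says that an interval including 1 will be read as safety. That is an inference. However, the plan states no other criterion for reaching the conclusion in Section 3.0.

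The study is meant to guide intraoperative practice. If inpatient MI, CVA or death is rare, an interval that includes 1 may also include a doubling of risk, and a null result would then be offered as reassurance it cannot give. Section 2.0 shows the investigators know that small numbers weakened earlier studies, yet nothing shows that 10,000 is enough for these outcomes.

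**Working it through.** **The plan's figure.** The 10,000 cannot be reproduced, because Section 8.0 gives no rate, effect, power or exposure split. One conventional set of assumed inputs comes close: reference rate 0.5%, odds ratio 2, 80% power, two-sided 5%, 1:1. It gives 9,504, or 10,296 with continuity correction. None of these inputs is in the documents, and that design would aim to detect a difference, not to rule one out.

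**Inputs.** From the plan: N = 10,000 and 95% intervals. Assumed, because the documents are silent:

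- Event rate p per outcome of 0.1%, 0.3%, 0.5% or 1%, which is 10, 30, 50 or 100 events.
- Exposed share s of 50% or 80%. The higher share is plausible for the <60 mmHg cut-off, since Section 2.0 says "many anesthesiologists routinely manage the blood pressure in the 40-60 mmHg MAP range".
- Odds ratio 2 as an illustration, not a proposed margin.

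All figures are unadjusted and use a single yes/no exposure.

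**Step 1: precision when the true odds ratio is 1.** SE(log OR) = 1/√[N·s(1−s)·p(1−p)]. The expected interval is exp(±1.96·SE). The chance that the upper limit falls below 2 is Φ(ln 2/SE − 1.96).

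Example, s = 0.5 and p = 0.1%: SE = 1/√(10,000 × 0.25 × 0.001 × 0.999) = 0.633. The interval is exp(±1.240) = 0.29 to 3.46. The chance is Φ(0.693/0.633 − 1.96) = Φ(−0.86) = 19%.

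| Rate (events) | 50% exposed: 95% CI | Chance upper limit <2 | 80% exposed: 95% CI | Chance upper limit <2 |
|---|---|---|---|---|
| 0.1% (10) | 0.29–3.46 | 19% | not given | not given |
| 0.3% (30) | 0.49–2.05 | 47% | 0.41–2.45 | 33% |
| 0.5% (50) | 0.57–1.74 | 69% | 0.50–2.00 | 50% |
| 1% (100) | 0.67–1.48 | 93% | 0.61–1.64 | 79% |

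At 0.1% with 80% exposed only 10 × 0.2 = 2 events are expected in the unexposed, too few for this approximation. Simulated binomial counts give 19%, 47%, 68% and 92% at 50% exposed. At 80% exposed they give 35%, 48% and 74% for the last three rates.

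**Step 2: events needed for an 80% chance of excluding 2.** This requires SE = ln 2/(1.96 + 0.84) ≈ 0.247. For rare events, events = 1/[SE²·s(1−s)].

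- 50% exposed: 66 (about 68 by simulation), or about 0.7% of 10,000.
- 80% exposed: 103 (about 119 by simulation), or 1.0% to 1.2%.

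A tighter margin needs more. At 50% exposed, a margin of 1.5 needs 191 events.

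**Step 3: power if risk truly doubles.** Here the rates above apply to the unexposed and the odds are doubled in the exposed. At 50% exposed this gives about 15, 45, 75 and 149 events in total. Two-sided Fisher exact power is:

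| Rate in unexposed | 50% exposed | 80% exposed |
|---|---|---|
| 0.1% | 18% | 7% |
| 0.3% | 56% | 34% |
| 0.5% | 80% | 57% |
| 1% | 98% | 89% |

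At 0.1% with 50% exposed, a real doubling would be non-significant 82% of the time.

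**Step 4: absolute scale.** The risk-difference half-width is 1.96·√[p(1−p)/(N·s(1−s))]. At 50% exposed with no true difference it is 0.12, 0.21, 0.28 and 0.39 percentage points for the four rates.

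**The case against.** The strongest reply is that the fault is inferred. The stated goal is neutral, the conclusion is hedged, and a reader of the report would see a wide interval for what it is. That is fair as to intent. It leaves the gap in place, since no threshold is set for judging the interval.

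Second, every magnitude rests on assumed rates and exposure shares, and the answer changes across the range: at 1% with half exposed, 10,000 is ample for excluding an odds ratio of 2. This stands. The omission is certain; its consequence depends on counts that only the investigators can supply. The 80% share is also loosely grounded, because Section 2.0 describes anesthesiologists rather than patients and says little about the <45 or <50 mmHg cut-offs.

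Third, the planned analysis concerns level and duration of hypotension, so one unadjusted split is only a rough guide to its precision. Adjustment and several cut-offs would generally reduce precision; a graded exposure could behave differently.

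Fourth, the relative scale shows rare events at their worst. A half-width of 0.12 percentage points, roughly 1 in 800, may be informative. This stands and is a reason to report risk differences, but a limit on that scale would also have to be set in advance.

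Finally, N may simply be the records available from the fixed window in Section 3.0. That is acceptable in a retrospective study, although Section 8.0 calls the number required. The point asks for stated precision, not for more patients.

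**Conclusion.** The concern holds. As written, the plan lets an inconclusive interval stand as support for Hypothesis A. Whether it would do so in practice depends on event counts. For an illustrative margin of 2, 10,000 patients are adequate if each outcome occurs in about 0.7% or more (half exposed) or about 1.0% to 1.2% or more (80% exposed). At 0.1% to 0.3% the chance of excluding a doubling when there is no effect is below one half in every scenario computed. These figures assume a single binary exposure and no adjustment. The missing margin, upper-limit rule and precision statement do not depend on those assumptions.

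This should be fixed before outcomes are analyzed. It does not stop the analysis from running, but it determines what the study can conclude.

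**What to change.** In Sections 3.0 and 4.0, restate Hypothesis A as an estimation question: how large an increase in inpatient MI, CVA or death do the data rule out? Then, in Section 8.0, in this order:

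1. Before any outcome is counted, state the largest acceptable increase, as an odds ratio or a risk difference. The value is for the investigators to choose and justify.
2. Conclude that there is no clinically important increase only if the upper 95% limit lies below that value. If neither that nor harm is shown, report the result as inconclusive.
3. Name one primary hypotension measure from Section 7.0 for this conclusion. The other MAP cut-offs and durations become secondary.
4. Report risk differences beside odds ratios.
5. Obtain the overall event count for each outcome without splitting by exposure, and state the expected interval width next to the 10,000.

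A composite of MI, CVA and death is optional.

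The cost is wording in three sections and one pooled count from the same records. The drawback is that individual rare outcomes may have to be reported as inconclusive. With an illustrative margin of 2 and 80% power, N = 1/[SE²·s(1−s)·p(1−p)] with SE ≈ 0.247 gives about 13,100 patients at 0.5% and 65,400 at 0.1% with half exposed. With 80% exposed it gives about 20,500 and 102,000. It is better to state that limit now than after the results are known.

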5.0 STUDY DESIGN

5.1 Endpoints

5.1.1 Primary Endpoint

The primary outcomes are the incidences of:

- i. myocardial infarction (MI)
- ii. cerebrovascular accident (CVA)
- iii. death
- iv. calculated perioperative intraoperative blood loss.

All primary outcomes are events during the inpatients stay.

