5.1.2 Secondary Endpoints

The secondary outcomes are incidences of:

- i. acute renal failure (ARF)
- ii. Pneumonia
- iii. Arrhythmia
- iv. deep venous thrombosis (DVT)
- v. pulmonary embolism (PE)
- vi. blood transfusion

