7.1 Data Collection

The following data will be collected:

Pre-operative/Baseline

- MRN
- Age
- Height
- Weight
- BMI
- ASA classification
- Ethnicity
- Gender
- Baseline status: METS, substance hx, smoking hx, SOB
- Comorbidity: OSA, COPD, asthma, HTN, CAD, CHF, Arrhythmia, pulmonary hypertension, seizure, TIA/CVA, renal dx, DM (type I or type II), coagulopathy, hx of dvt/PE
- Pre-op medications: beta-block, asa, anti-coagulant, nsaid, steroids
- Blood pressure: pre-op BP, and all intra-op

Intra-Operative

- Blood pressure: pre-op BP and all intra-op
- Intra-op medications: TXA IV or topical, ketamine, blood transfusion, albumin, IV fluids, epinephrine, ephedrine, phenylephrine, hydralazine, labetalol

Post-Operative

- Laboratory results: hemoglobin, BUN, creatinine

- Post-operative medications: (first 24 hours) IV fluids, albumin, blood transfusion, epinephrine, ephedrine, phenylephrine
- Complications: MI, CVA, death, ARF, pneumonia, arrhythmia, DVT, PE

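### MI, CVA and death are counted only up to a variable discharge that follows the exposure; length of stay is not collected, and the possible safety conclusion is not limited to in-hospital events

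*Combined protocol and SAP*

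**What the plan says.** Section 5.1.1 names MI, CVA, death and calculated blood loss as primary outcomes and adds: "All primary outcomes are events during the inpatients stay". It gives no number of days. Section 5.1.2 opens with "The secondary outcomes are incidences of" and gives no window at all.

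The exposure in section 7.0 is intraoperative: "The independent variables of interest include extent of intraoperative hypotension (MAP <45, 50, 55, 60 mmHg) and duration of hypotension (5 mins interval").

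Section 7.1 lists the post-operative events as "Complications: MI, CVA, death, ARF, pneumonia, arrhythmia, DVT, PE", again without a window. The synopsis collects durations of surgery and of anesthesia ("duration of anesthesia"). Neither list contains length of stay, discharge date or readmission. Section 8.0 plans two-step logistic regression for odds ratios with 95% confidence intervals and does not mention time at risk.

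Hypothesis A in section 4.0 is one of no effect: "There is no association between level and duration of hypotension with (i) myocardial infarction (MI), (ii) cerebrovascular accident (CVA), (iii) death". Section 3.0, repeated in the synopsis, says the study will show whether practice needs to change, "or conversely may allow us to argue that deliberate hypotensive neuraxial anesthesia is not associated with adverse events".

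**The concern.** When events are counted only until discharge, a patient's chance of a recorded event depends on how long the patient stays as well as on the underlying risk. Discharge happens after the exposure and may be influenced by it. The protocol itself presents hypotension as a way to reduce blood loss, and blood loss could plausibly affect how soon a patient goes home. If stay differs across hypotension categories, the odds ratios mix a difference in risk with a difference in observation time.

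Two things are at stake. First, the data as listed would not let anyone see whether this has happened. Second, a null result for in-hospital events could be reported as absence of association with adverse events generally, although nothing after discharge would have been counted for MI, CVA or death.

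**Working it through.** **Plan's own figure.** There is none to reproduce. The only number in section 8.0 besides the confidence level is the sample size of 10,000, and no event rate, length of stay or follow-up time goes with it. The arithmetic below is illustration under stated assumptions.

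**Step 1. Can time at risk be recovered from the planned data?**

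- End of observation: discharge (5.1.1).
- Start of exposure: during surgery (7.0).
- Durations collected: surgery and anesthesia (synopsis). Section 7.1 lists no durations.
- Length of stay, discharge date, readmission: in neither list.
- Model: logistic regression, no time-at-risk handling (8.0).

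As written, unequal observation can be neither checked nor allowed for.

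**Step 2. How large could the distortion be?** For rare events the odds ratio is close to the risk ratio, so

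observed ratio = true ratio × C(L1) / C(L0),

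where L1 and L0 are the mean stays in the exposed and unexposed groups and C(L) is proportional to the share of events captured by day L. Everyone in a group is treated as having the group's mean stay.

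- Constant daily hazard: C(L) is proportional to L, so the factor is L1/L0.
- Hazard declining exponentially with a mean of 3 days: C(L) = 1 − exp(−L/3).

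The stays and hazard shapes are assumptions. With L0 = 3, C(3) = 1 − exp(−1) = 0.632.

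- L1 = 2: constant 2/3 = 0.67; declining 0.487/0.632 = 0.77.
- L1 = 4: constant 4/3 = 1.33; declining 0.736/0.632 = 1.16.

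| Mean stay, exposed vs unexposed (days) | True ratio | Observed, constant hazard | Observed, declining hazard |
|---|---|---|---|
| 2 vs 3 | 1.0 | 0.67 | 0.77 |
| 2.5 vs 3 | 1.0 | 0.83 | 0.89 |
| 3 vs 3 | 1.0 | 1.00 | 1.00 |
| 3.5 vs 3 | 1.0 | 1.17 | 1.09 |
| 4 vs 3 | 1.0 | 1.33 | 1.16 |
| 2 vs 3 | 1.5 | 1.00 | 1.15 |
| 4 vs 3 | 1.5 | 2.00 | 1.75 |

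The distortion can run either way, vanishes when stays are equal, and is smaller when risk is concentrated soon after surgery. In the 2 versus 3 day case, a true ratio of 1.5 would be hidden or nearly hidden.

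**Step 3. Does it reach all primary outcomes?** Blood loss is calculated from pre-operative and post-operative hemoglobin (7.0), and the synopsis specifies the first post-operative value. That measurement depends little on when the patient leaves. The point concerns MI, CVA and death.

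**Step 4. Does the conclusion match the window?** The data for MI, CVA and death cover the stay. The possible conclusion in section 3.0 and the synopsis refers to adverse events without limit of time. No section narrows it.

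**Step 5. Is a longer window compatible with the dates?** Surgeries run to December 3, 2018 (3.0), and the protocol version is dated 12/5/2018. Thirty days after December 3, 2018 is January 2, 2019, so the last patients would not have complete 30-day follow-up until then.

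**The case against.** The best defence is that an inpatient window is a legitimate choice, openly stated, that it suits an intraoperative exposure, and that it restricts counting to the period when the hospital observes the patient directly. The documents give no lengths of stay and no evidence that stay varies with hypotension, so the distortion is hypothetical. This stands as far as the window goes: the inpatient analysis need not be abandoned. It does not answer the missing discharge data or the unrestricted conclusion.

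Four stronger readings are tempting, and the documents do not support them.

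- A reader might infer that every outcome stops at discharge. The restriction is stated for the primary outcomes only. For the secondary outcomes, including DVT and PE, the window is simply not given.
- A reader might infer that the study sets out to declare the technique safe. Section 3.0 says the results may allow that argument, as one of two possible outcomes, although hypothesis A is itself a no-association hypothesis.
- A reader might infer that the bias favours hypotension through earlier discharge. Step 2 shows that the opposite is equally possible.
- A reader might infer that 30-day events are available from the same record system. The documents say that EPIC was introduced in 2016 and that the MRN is collected. They do not say that patients with later events return to this hospital or that deaths after discharge are recorded there.

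**Conclusion.** The concern holds in limited form. For MI, CVA and death, observation ends at a variable, post-exposure discharge; the planned data and model give no means of detecting or handling unequal observation; and the possible conclusion is wider than the window. These three statements rest on the text alone.

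The size of any bias is unknown. The ratios of 0.67 to 1.33 under no true effect depend on assumed mean stays of 2 to 4 days in the exposed group against 3 days in the unexposed, and on the assumed hazard; the declining hazard narrows the range to 0.77 to 1.16. They show that a modest difference in stay could matter, not that it will. The plan should be changed because the remedy is nearly free and alters what the study can properly conclude.

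**What to change.** 1. Add admission and discharge dates to the data lists in the synopsis and section 7.1, and report length of stay by hypotension category.
2. Keep the inpatient analysis. Add a sensitivity analysis counting MI, CVA and death in a fixed early post-operative window that nearly all patients complete in hospital. Choose it from the length-of-stay distribution before looking at events by exposure, and report how many patients in each category leave before it ends. Entering length of stay as an ordinary covariate is not a substitute, because it follows the exposure and an event can itself change the stay.
3. In section 3.0 and the synopsis, state the conclusion as applying to in-hospital events.
4. In section 5.1.2, state the ascertainment window for the secondary outcomes.
5. Optional, only if the sponsor confirms that later encounters and deaths under the same MRN can be retrieved: a supplementary 30-day analysis counted from surgery and labelled a lower bound, since events treated elsewhere would be missed. Extract the data after January 2, 2019, or end the surgery period earlier.

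The cost of items 1 to 4 is the extra date fields, a little more analysis and a narrower conclusion. The fixed-window analysis will count fewer events, so its intervals will be wider; it serves as a check on the main result.
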